1 PROTOCOL SUMMARY

1.1 SYNOPSIS

Title:	Preventing Diabetes in the Deep South: Extending Partnerships and Adapting Interventions to Reach Rural Communities at High Risk
Study Description:	Alabama has the 3rd highest rates of diabetes in the United States. The prevalence of diabetes is 14.1% compared with 9.4% nationally; in some areas of the Black Belt, the prevalence is over 20%, or 1 in 5 adults. Roughly 37% of people living in Alabama have pre-diabetes, but only 10% of these individuals know they have it. The Diabetes Prevention Program (DPP) is an evidence-based intensive lifestyle intervention that targeted weight loss and successfully reduced diabetes risk by 58%. However, the DPP was a resource intensive efficacy trial and was not designed to be directly deliverable in real world settings. Community-based adaptations of the Diabetes Prevention Program (DPP) can be feasible but typically fail to show the same benefit as the more intense original trial version of the lifestyle program. The aim of this study is to introduce innovative design elements to a community-based adaptation of the DPP to enhance research effectiveness. To reduce or delay the onset of diabetes among high-risk populations, the American Diabetes Associations recommends taking metformin. "Metformin therapy for prevention of type 2 diabetes should be considered in those with prediabetes, especially for those with $BMI > 30 \text{ kg/m}^2$, those aged < 60 years, and women with prior gestational diabetes mellitus." ¹ We will compare two strategies, lifestyle modification alone versus lifestyle modification plus metformin recommendation, in a group-randomized controlled 2-arm trial.
Objectives:	Conduct a 12-month randomized control trial (RCT) to determine the feasibility of implementing a peer coach-facilitated DPP delivered by telehealth. The DPP will be compared to DPP with metformin therapy recommendations. The goal of the intervention is to prevent or delay the

	Type 2 diabetes among rural primary care patients with pre-diabetes and obesity at high risk for developing diabetes. The primary outcomes are body weight and HbA1c results at month 12. The RCT will test feasibility and provide data that will inform design and power for a future study to assess diabetes prevention as the main outcome measure.
Endpoints:	Percent change in body weight and HbA1c results at month 12
Study Population:	Enroll 100 adults with obesity (BMI >30kg/m ²) aged 19 to 65 years who receive primary care at one of four partnering clinics in rural Alabama.
Description of Study Intervention:	Condition 1. Receive lifestyle modification alone (DPP) Condition 2. Receive lifestyle modification with metformin therapy recommendations (DPP-recommendations)
Study Duration:	3 years
Subject Duration:	12-months

2 INTRODUCTION

2.1 SPECIFIC AIMS

Conduct a pilot study of an innovative lifestyle program (telehealth + community health workers) with and without metformin for diabetes prevention. This pilot trial is intended to consolidate and refine operations within the primary care coalition, and to develop data for a larger scale randomized trial evaluating a novel and sustainable approach for diabetes prevention that involves an innovative lifestyle intervention combined with metformin. The current revision application underscores the commitment of the DRC to partnerships and research that is directed at improving health in patients with diabetes and cardiometabolic disease in our communities with a particular emphasis on health disparities in rural communities. The primary care coalition is designed as a powerful resource for the study of mechanisms responsible for chronic disease disparities and developing interventions uniquely effective in these high-risk populations.

2.2 BACKGROUND AND SIGNIFICANCE

Alabama has the 3rd highest rates of diabetes in the U.S with 14.1% of adults living with diabetes compared with 9.4% nationally. Diabetes can be delayed or prevented for some people by making changes to their lifestyle. People at high risk for developing diabetes, often have prediabetes. Prediabetes is when a person has higher than normal blood sugars but do not yet have diagnosed diabetes. Roughly 37% of people living in Alabama have prediabetes, but only 10% of these individuals know they have it. Lifestyle interventions that include weight loss, increasing physical activity, and changing eating habits have been shown to prevent diabetes among some people. The Diabetes Prevention Program (DPP) provided a tested model of an intensive lifestyle intervention that targeted weight loss and successfully reduced diabetes risk by 58%. However, the DPP was a resource intensive efficacy trial and was not designed to be directly deliverable in real world settings. Community-based

adaptations of the DPP can be feasible but typically fail to show the same benefit as the more intense original trial version of the lifestyle modification program. The DPP demonstrated benefit from metformin therapy for prevention but to date limited effort has been made to promote the use of metformin therapy for diabetes prevention. Given the urgent need for novel ways to prevent or delay the Type 2 diabetes, this trial will combine the DPP with novel components including telehealth and peer coaches. PreventT2 is a CDC-adapted DPP implemented nationally at a variety of community locations including primary care offices, non-profits, and healthcare organizations (<https://www.cdc.gov/diabetes/prevention/index.html>) PreventT2 will be implemented in both arms of this study to assist participants at high risk of developing diabetes in making lifestyle modifications that may prevent or delay onset of Type 2 diabetes. In this trial, Condition 1 (lifestyle modification only) will be compared to Condition 2 which includes lifestyle modification with the recommendation that the primary care provider consider adding a prescription for metformin. The aim of this study is to introduce novel design elements including telehealth delivery, peer coaches, and daily weight checks to a community-based adaptation of the DPP to enhance research effectiveness. This approach may potentially prove to be a cost-effective and scalable approach to diabetes prevention in the Alabama Black Belt.

3 OVERVIEW OF STUDY DESIGN

This study is a cluster-randomized, two-arm controlled trial in primary care settings. A total of 4 primary care clinics in rural Alabama will be randomized to either 1) Receive lifestyle modification alone (DPP) or 2) Receive lifestyle modification with metformin therapy recommendations (DPP-recommendations). The sample will include up to 100 adults with obese (BMI 30-50 kg/m²) patients (4 clinics, 25 patients / clinic).

The primary aim of this trial is to conduct a 12-month randomized control trial (RCT) to determine the feasibility of implementing a peer coach-facilitated DPP delivered by telehealth. The DPP will be compared to DPP with metformin therapy recommendations. The goal of the intervention is to prevent or delay the Type 2 diabetes among rural primary care patients with pre-diabetes and obesity at high risk for developing diabetes. The primary outcomes are body weight and HbA1 results at month 12. The RCT will test feasibility and provide data that will inform design and power for a future study to assess diabetes prevention as the main outcome measure. All participants will receive the lifestyle intervention of the Diabetes Prevention Program (DPP) plus telemonitoring of their body weight using an Ideal Life body weight scale. The DPP is a 12-month intensive lifestyle modification intervention that includes 16 group-based sessions over 6-months and 6 group-based sessions in the remaining 6-months. Consistent with the DPP, content includes fundamental components of evidence-based lifestyle interventions, including recommendations for dietary modification, increased physical activity, and behavioral strategies designed to promote treatment adherence. The current intervention includes two new features, a telemedicine platform and the participation of community health workers. Participants will be partnered with a Community Health Worker (CHW) who will facilitate the delivery of the group-based session delivered by a trained nurse or dietitian joining via the telehealth platform. The CHW will assist participants in setting up the telemonitoring and conduct 16 brief weekly calls and 6 monthly calls over the 12-month intervention.

The primary outcome measures include feasibility assessment and the measurement HbA1c and body weight at baseline, 6 months, and 12 months. Demographic characteristics will be collected at screening and baseline. Participants will be enrolled for one-year period. This is a pilot trial designed to test feasibility for a larger scale randomized clinical trial that will evaluate effectiveness of an innovative lifestyle intervention combined with metformin in for diabetes prevention.

4 INCLUSION/EXCLUSION CRITERIA

Prevent T2 is a pragmatic trial to be conducted in primary care clinics. Thus, the inclusion criteria are broad and designed to capture a large cross-section of the target population.

4.1 INCLUSION CRITERIA

- Age 19 (the age of adulthood in Alabama) to 65 years
- A1c (A1c) 6.0% to 6.4%
- Body mass index (BMI) 30-50 kg/m²
- Receives care at one of the 4 participating primary care clinics
- Resides in one location at least 5 days each week
- Telephone line or Wi-Fi internet connection or cellular signal in home
- Willing or able to partner with a Community Health Worker
- Willing to attend group sessions

4.2 EXCLUSION CRITERIA

- Pregnancy or anticipating pregnancy
- Diabetes (A1c $\geq 6.5\%$, and/or chart value of fasting glucose ≥ 126 mg/dl, and/or diabetes medications)
- Unwilling or unable to do any of the following: give informed consent, accept random assignment, allow study staff to visit them at their primary care clinic for two follow-up visits
- Likely to relocate and no longer be seen at primary care clinic in the next 2 years
- Weight loss or gain $\geq 5\%$ of body weight in past 6 months (other than postpartum)
- Prescription weight loss medications within the past 6 months
- Another household member already participating in the study
- Abnormal thyroid status
- eGFR ≤ 60
- not able to ambulate or have end-stage medical conditions with limited life expectancy

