4.4 STRATEGIES FOR RECRUITMENT AND RETENTION

Recruitment from four primary care clinics in the AL Black Belt will be in a manner similar to that used for our previous trials implemented in primary care, including our ongoing Southeastern Collaboration to Improve Blood Pressure" in which we have currently enrolled 660 patients from 31 primary care clinics in the Black Belt. We will begin by conducting chart reviews and send direct mailings to practice lists of potentially eligible patients that include opt-out postcards providing a brief study description and contact information followed by recruitment phone calls after 2 weeks. In our experience, this strategy yields by far the highest return. We will also place flyers in accessible, high-traffic areas (e.g., waiting

room, exam rooms) and provide practice staff with simple and brief forms to refer patients. We will also conduct periodic 'lunch and learn' seminars for practice staff to facilitate referrals. Given our significant experience recruiting from primary care, the high prevalence of pre-diabetes and obesity in the rural south, and the strong interest in weight management programs in general, we do not anticipate difficulty recruiting and enrolling the required number of participants. The text of all announcements and advertisements and all recruitment methods will have IRB approval prior to use. Solicitation of information from candidates will be conducted in a HIPAA-compliant manner. A trained recruiter will follow up with the patient to assess their interest in participating and screen them for eligibility during a screening visit (SV) in which they will have a point-of-care A1c conducted and answer a screening questionnaire to determine their eligibility. Following the completion SV activities, if the patient is deemed eligible, he/she will provide written informed consent prior to participating in baseline measurements to formally enrolled in the study at the baseline visit. Patients who participate in the SV activities will not be considered enrolled in the study until they have provided informed consent and completed baseline measurements. Patients may choose to complete the baseline measurements at the SV or schedule an appointment to conduct baseline measurements.

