5 RANDOMIZATION/BLINDING

Randomization. This is a cluster-randomized trial, and enrolled patients at a given clinic will receive the intervention assigned to their clinic. A total of 4 primary care clinics in rural Alabama will be randomized to either 1) Receive lifestyle modification alone (DPP) or 2) Receive lifestyle modification with metformin therapy recommendations (DPP-recommendations).

Blinding. Given that this trial is a small pilot randomized at the clinic level and the interventions are very distinct, patients will know their group assignment, as will clinic staff, CHWs, and research staff that are involved in delivering the intervention.

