6.1.2 DESCRIPTION OF LIFESTYLE INTERVENTION WITH METFORMIN THERAPY RECOMMENDATIONS ARM

Lifestyle intervention program (telehealth + peer coach) with metformin therapy recommendations (DPP-recommendations): Participants will receive the same lifestyle intervention as those in the DPP condition described above. In addition to the lifestyle intervention, they will receive a recommendation for metformin therapy for prevention of type 2 diabetes. Primary care providers at the practices randomized to the DPP-recommendations condition will attend an orientation session and evidence-based materials about low-dose metformin therapy recommendations for patients with pre-diabetes to prevent or delay the onset of type 2 diabetes. At the baseline assessment, study staff will provide participants with the patient education handout on “Understanding Metformin for Pre-diabetes” that details using metformin for prevention of type 2 diabetes. At the same time, the participant’s primary care provider will receive a recommendation to provide their patient with a prescription for Metformin for diabetes prevention. The communication between study staff and PCPs will be developed and

tailored to fit the work flow of each clinic. As described in the inclusion/exclusion criteria, participants without a charted eGFR or an eGFR<60 within the last 6-months will be excluded from the study.

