Baseline Measurements. After individuals have been recruited and screened, eligible patients will be invited to enroll and complete baseline assessments. This visit will include completing informed consent to participate in the study and completion of surveys. Baseline assessments will be conducted by trained recruiter at the patient's primary care clinic. Completion of the baseline assessment will take approximately 30 minutes to 60 minutes. Surveys may be completed in-person during the visit or at a later time over the phone. Upon completion of baseline assessments, they will receive specific information and materials relevant to the condition to which they have been assigned (described above). Study personnel will review these materials with participants during this study visit. It is anticipated that the review of intervention procedures and materials will take approximately 30 minutes to 60 minutes. Follow-up assessments will be conducted in a similar manner as described in bullet below.

Weight

Weight is the primary outcome for this study and will be measured with the patient in light indoor clothes without shoes to the nearest 0.1 kg using a digital scale at each assessment visit. Patients will be

instructed to stand still in the middle of the scale with head erect and eyes looking straight ahead. After the weight is recorded, the patient will step off of the scale and the research assistant will set the scale to zero, then repeat and record the second weight measurement. If the two readings differ by more than 0.5 kg, a third measurement will be obtained. The closest two measurements will be averaged for analysis. The accuracy of the scales will be checked at scheduled monitoring visits using standard weights. Weight will be measured at the baseline visit, and at the 6 and 12 month assessment visits.

Height

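### Clinics are randomised, but the plan describes no allocation concealment while patients are referred and consented, so who enters can differ by arm

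*Combined protocol and SAP*

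**What the plan says.** - **Unit of randomisation.** Section 5 randomises four clinics and states that "enrolled patients at a given clinic will receive the intervention assigned to their clinic". Section 12 puts two clinics in each arm, with 25 patients per clinic.
- **Entry criterion.** Section 4.2 excludes anyone unwilling or unable to "give informed consent, accept random assignment, allow study staff to visit them at their primary care clinic".
- **Who knows the arm.** Section 5 says "patients will know their group assignment, as will clinic staff, CHWs, and research staff that are involved in delivering the intervention". The last clause limits the research staff covered to those who deliver the intervention.
- **Routes of entry.** Section 4.4 begins with chart review and mailing, which it calls the highest-yield strategy. It adds flyers and seminars for practice staff, and will "provide practice staff with simple and brief forms to refer patients".
- **Provider knowledge.** Section 6.1.2 says "Primary care providers at the practices randomized to the DPP-recommendations condition will attend an orientation session". The patient's metformin handout and the recommendation to the provider are both issued at the baseline assessment.
- **Order at the baseline visit.** Section 7 says of it: "This visit will include completing informed consent to participate in the study and completion of surveys". Then: "Upon completion of baseline assessments, they will receive specific information and materials relevant to the condition to which they have been assigned". Baseline may be done on the same day as screening (Sections 4.4 and 7).
- **Analysis.** Section 13 uses a mixed model with practice as a random effect. Adjustment for baseline values appears only in secondary models.

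The documents do not say when clinics are randomised relative to patient identification. They describe no concealment of the allocation from patients, referring staff or recruiters before consent.

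**The concern.** In a cluster trial, randomising clinics protects the patient-level comparison only if patients enter each clinic by a process unaffected by its arm. Here staff who know the arm can influence who is referred, and patients may consent knowing which single arm they will get. The acceptance criterion may then test willingness to join one known arm, and that arm differs between clinics. Criteria that need judgement, such as likely relocation or willingness to work with a community health worker, add some room for this.

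If the recommendation arm recruited patients who differ in motivation or in openness to medication, the difference could be read as an effect of the recommendation. Estimates of uptake and retention would also describe a selected group, and the pilot exists to inform the design and power of a larger trial. Two clinics per arm cannot be relied on to average such differences out, and measured baseline values would capture motivation only partly.

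**Working it through.** **Timing check.**
1. Arm materials are handed over at each patient's baseline visit (Section 7), and in the recommendation arm the provider is contacted at the same time (Section 6.1.2). A clinic's arm must therefore be known to study staff by the end of its first baseline visit.
2. Consent is completed at that same visit, before the materials are given.
3. Assuming individual, successive visits, only the first patient at a clinic could consent before the arm is in use there: 25 − 1 = 24 per clinic, and 4 × 24 = 96 of 100 overall. Several visits on one opening day would lower this slightly. Section 6.1.1 describes rolling delivery, which does not suggest one batch consented before allocation.
4. For referral and screening no such deduction is possible, because neither the randomisation nor the provider orientation is dated.

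**The plan's own precision (Section 12), reproduced.** D = 1 + ICC × (m − 1), with ICC 0.01.
- m = 25: D = 1.24, and 50 / 1.24 = 40.3 (stated 40).
- m = 20: D = 1.19, and 40 / 1.19 = 33.6 (stated 33).
- Half-width for one arm's mean change, t / √n: 0.284 SD at n = 50 and 0.351 SD at n = 33.6. These match the stated ±0.28 and ±0.35, although the lower figure uses the unclustered 50. At an effective n of 40 it would be 0.31 (normal) to 0.32 (t).

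These describe one arm. For a difference between two equal arms, multiply by √2: 0.28 × 1.414 = 0.40 and 0.35 × 1.414 = 0.49 SD. This makes no further allowance for having only four clinics.

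**Illustrative selection bias.** All inputs here are assumptions; none is in the documents. Let willingness be a standard normal score and let the most willing fraction consent: p = 0.6 to 0.7 in the lifestyle-alone arm, q = 0.3 to 0.5 in the recommendation arm. Willingness correlates r = 0.2 to 0.5 with 12-month weight change.

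Arm difference due to selection = r × [φ(z_q)/q − φ(z_p)/p], in SD units.

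| Fraction consenting | Mean willingness of those who consent |
|---|---|
| 0.7 | 0.497 |
| 0.6 | 0.644 |
| 0.5 | 0.798 |
| 0.3 | 1.159 |

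- Smallest: p = 0.6, q = 0.5, r = 0.2 gives 0.2 × (0.798 − 0.644) = 0.03 SD.
- Largest: p = 0.7, q = 0.3, r = 0.5 gives 0.5 × (1.159 − 0.497) = 0.33 SD.

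Across these ranges the bias stays below the 0.40 to 0.49 SD half-width, though at the top it is a large part of it. Recruiting more patients would narrow the interval without reducing the bias.

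**The case against.** Several points on the other side stand.

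- **Selection by metformin is weaker than it may look.** Taking metformin is not a condition of entry to the recommendation arm. The provider is asked to consider a prescription (Section 2.2), and patients who do not tolerate the drug stay in follow-up (Section 10.1). A patient who does not want it can still enrol and receive the same lifestyle programme.
- **Direction is open.** An offer of medication might raise consent rather than lower it.
- **Much of recruitment is protected.** The A1c, BMI, age and eGFR limits are objective and the same in both arms. Chart review with mailing is the main route, and staff referral is secondary.
- **This is a pilot.** Section 12 justifies the sample by feasibility and the precision of estimated changes, with no powered comparison of arms. Section 13 summarises patient characteristics by arm and has secondary baseline-adjusted models, and Section 11 provides quarterly review of accrual and eligibility.

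A reader might also infer that the recruiter is unblinded, because the recruiter both screens and conducts baseline assessments. Section 5 names only research staff who deliver the intervention, and Section 7 has study personnel, not specifically the recruiter, review the arm materials. The documents leave the recruiter's status open.

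These points limit the likely size of the problem. They do not supply concealment, and openly declared delivery does not address recruitment after allocation.

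**Conclusion.** The concern holds as a gap in concealment that is cheap to close. That most patients consent once the arm is in use at their clinic follows from the order of steps, assuming individual baseline visits. That clinic staff both know the arm and refer patients is stated in the plan.

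A reader might go further and conclude that the arm is already known at referral and screening. That is plausible, but it is an inference, since clinic randomisation is not dated. Nor do the documents show that selection has a particular direction, or that the wording of the acceptance criterion is itself the defect.

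The size is unknown. The 0.03 to 0.33 SD range rests wholly on assumed consent rates and correlations, and should be set against about 0.40 to 0.49 SD for the arm difference, not against the plan's per-arm 0.28 to 0.35 SD. The change should be made, but the pilot's feasibility aims do not fall without it.

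**What to change.** 1. **Patient lists.** State when clinics are randomised. Complete chart review and fix each clinic's list of potentially eligible patients before allocation is disclosed, and route staff referrals through the same list. If clinics are already allocated, build the lists by one rule without reference to arm. Patients who become eligible later enter by a list refresh under that rule.
2. **Consent.** Use one IRB-approved script describing both conditions. Do not disclose the clinic's arm to the patient, or to the recruiter where feasible, until consent and baseline measures are complete. Section 7 already places the arm materials after baseline.
3. **Recruitment log.** Record and report eligible, approached, refused (with reasons) and enrolled patients by clinic and arm.

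Rewording the criterion to willingness to take part under either study arm is optional; it only supports item 2.

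**Cost.** Mostly a re-ordering of planned steps plus a log, with no added patients. Chart review must finish before allocation is disclosed, and the consent wording needs IRB agreement. Concealment will be imperfect, since clinic staff who know the arm may still mention it; the log would help to show differences in refusal or enrolment.
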